10.3 Analysis Populations

With the exception of the assessment of vital status until the formal close of the study, the statistical analyses or summaries for efficacy and safety parameters will include evaluations performed from randomization up to the date of the subject's last study visit or 30 days after the permanent discontinuation of study drug. Any additional evaluations will be included in the data listings only.

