10.3.3 Safety Population

The safety population will contain any subject randomized into the study who receives any amount of study drug. Safety analyses or summaries will include all available data, as appropriate.

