10.11 Safety Endpoints

10.11.1 Adverse Events

Adverse events will be recorded throughout the study and at early termination. Adverse events and medical conditions will be coded using the Medical Dictionary for Regulatory Activities (MedDRA) coding dictionary. Treatment-emergent adverse events will be defined as those events, which are newly occurring or worsening from baseline. In all cases only treatment emergent adverse events will be summarized.

Treatment-emergent adverse events will be summarized by treatment group as the number and percentage of subjects having any treatment-emergent AE, having an AE in each body system, and having each individual AE. (*Note: In any given category [e.g., body system] a subject will only be counted once.*) Adverse events will further be categorized by severity, relationship to study drug, and action taken. Other information collected will be listed, as appropriate.

Any event starting more than 5 days after the final dose of study drug will be excluded from the above described tables and only listed, unless the event caused discontinuation from the study

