This SAP is based on study protocol, United States (US) Amendment 2 (dated 15 October 2014) and Israel Amendment 1 (dated 13 April 2015). It supersedes the statistical considerations identified in the study protocol. Any major deviations in this SAP from the statistical considerations of the protocol will be described and justified within the CSR. Lung Biotechnology (the sponsor) will follow this SAP in analyzing the study data. If during the course of the trial, the protocol or the set of Case Report Forms (CRFs) is modified in a way that affects the planned statistical analyses, a revised version of the SAP will be developed.

Only minor changes in the analyses shall be applied following the final version of the SAP. The CSR shall document minor changes.

Separate SAPs will be written to address the exploratory objectives of the hemodynamic, the plasma concentrations, and the exposure-response analysis for safety and efficacy endpoints.

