6.4.2 Handling of Missing Data

The sponsor acknowledges the implications of missing data on the integrity of study outcomes and, consistent with Fleming's recommendations (2011), implemented the following strategies to minimize the extent of missing data:

1. All subjects were allowed to continue in the study until the close of study, whether on IMP or not. Subjects were not to be summarily discontinued from the study, unless 1) the subject withdrew informed consent; 2) the subject met a primary endpoint and declined continuation in the study; or 3) the subject continued to be non-adherent to study protocol after repeated attempts to correct (at least 6 months). However, the subject has the right to discontinue from the study at any time. All subjects who discontinue the study, unless they withdraw informed consent, will continue to be followed, to the extent possible, for vital status until the sponsor concludes the study.
2. Recent publications (Sitbon et al., 2015; Galiè et al., 2015) have shown that roughly 20% of subjects prematurely terminate from mortality and morbidity studies in PAH. The sponsor has throughout the study engaged with study investigators to encourage subjects' retention in the study, adherence with the protocol, and compliance with IMP.
3. While the study protocol is necessarily complex in order to obtain the scientific data to evaluate the safety and efficacy of the IMP, the sponsor designed the protocol in the manner that was not burdensome to the subjects: 1) Much of the data collected for secondary endpoints is derived from assessments performed for 'standard of care' visits; 2) Study visits are minimal (quarterly) with permissive visit windows (\pm 10 days); 3) Use of optional substudies for exploratory endpoints; and 4) Sponsor-provided Tyvaso to all subjects in the study.

Methods for handling missing data will be described in the sections discussing each outcome.

No imputation is planned for missing safety or exploratory data.

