6.12 Primary Efficacy Analysis

As described in Section 2.1, the primary efficacy outcome is the TtCW, measured in days, where clinical worsening is defined as the first occurrence of any of the following:

- Death (all causes)
- Hospitalization due to worsening PAH
- Initiation of a parenteral (infusion or sub-cutaneous) prostacyclin directly related to worsening PAH
- Disease progression

- Unsatisfactory long-term clinical response

As described above, a blinded Event Adjudication Committee (EAC) will review all suspected clinical worsening events and make a final determination for each (see [Appendix 1](#)). The EAC Charter, Version [REDACTED], specifies evidence to be provided to the EAC along with the general rules and criteria for EAC confirmation of a primary endpoint of clinical worsening. Because the EAC Charter cannot address every possible scenario, the EAC Charter shall be viewed as a framework under which the EAC will operate. Each case will be determined on the basis of a consensus of the EAC, the members of whom are independent experts in PAH. Please see [Appendix 2](#) for general rules and criteria excerpted from the EAC Charter.

Subjects were not required to discontinue from the study after meeting a primary endpoint; thus, more than one clinical worsening event may be reported for the same subject. This section defines the calculation of time to each component of the primary outcome. The protocol specifies that investigators follow each subject for 30 days after the subject discontinues from the study to assess the occurrence of SAEs and for 90 days after the subject stops study medication for vital status. Further, the investigators are instructed to provide all clinical worsening events that occur after the primary clinical worsening event, as well as the vital status of all subjects at the time the sponsor terminates the study.

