7.2.1 Treatment-Emergent Adverse Events

A treatment-emergent adverse event (TEAE) is defined as any event not present prior to the initiation of the IMP or any event already present that worsens in either intensity or frequency following exposure to the IMP.

Only TEAEs occurring after IMP exposure will be summarized. Any AE starting prior to the first dose of IMP (i.e., during the screening period) will be excluded from the summary analyses.

The following notes the planned presentations of TEAEs. Other presentations for TEAEs may be produced to support the sponsor's review and analyses of events of special interest.

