7.2.7 Summary of Treatment-Emergent Adverse Events

A summary of all TEAEs will present numbers and percentages of the following by treatment group:

- Subjects with at least one TEAE
- Subjects with at least one IMP-related TEAE
- Subjects with at least one TEAE related to PAH background medication
- Subjects with at least one serious TEAE

- Subjects with a TEAE leading to permanent discontinuation of IMP

7.2.8 **Subjects with a TEAE leading to dose modifications of IMP Summaries of Adverse Events**

TEAEs will be separately summarized by treatment group for the following:

- Total number of TEAEs, total number subjects with at least one TEAE
- TEAEs by severity
- TEAEs by relationship to IMP
- TEAEs by relationship to PAH background medication
- TEAEs by action taken with IMP
- TEAEs leading to study withdrawal

TEAEs will be presented in alphabetical order of SOC and by decreasing order of incidence of the preferred terms.

For these summaries, a subject having the same TEAE multiple times will only be counted once for the corresponding preferred term. Similarly, a subject who experienced multiple TEAEs within the same SOC will be counted only once for that SOC.

A subject experiencing the same TEAE multiple times or at multiple severities will only be counted once under that preferred term at the worst severity rating. Similarly, a subject who experiences the same TEAE multiple times or at multiple severities across multiple preferred terms within the same SOC will only be counted once for the worst severity rating within the SOC.

A subject experiencing the same TEAE multiple times or at multiple relationships to IMP will only be counted once for the worst relationship to IMP within a preferred term. Similarly, a subject who experiences the same TEAE multiple times or at multiple relationships to IMP across multiple preferred terms within the same SOC will only be counted once for the worst relationship to IMP within the SOC. The same procedure will be used for relationship to PAH background medication.

A subject experiencing the same TEAE multiple times or at multiple actions taken to IMP will only be counted once for the worst action taken with IMP within a preferred term. Similarly, a subject who experiences the same TEAE multiple times or at multiple actions taken to IMP across multiple preferred terms within the same SOC will only be counted once for the worst action taken to IMP within the SOC.

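### The SAP gives treatment-emergent adverse events a start but no end tied to the last dose, so events in off-drug follow-up enter the by-arm TEAE tables

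*SAP*

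**What the plan says.** **SAP.** Section 7.2.1 defines a TEAE as "any event not present prior to the initiation of the IMP or any event already present that worsens" in intensity or frequency after exposure. Its one exclusion by time is for events that begin before the first dose. Section 7.2.7 then counts, by treatment group, "Subjects with at least one serious TEAE" and several other TEAE categories. Sections 7.2.8 and 7.2.9 break TEAEs down by severity, relationship, action taken and subgroup. None of them adds an end date, and 7.2.8 has no breakdown by seriousness.

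**Protocol.** Section 10.11.1 does set an end for the tables: "Any event starting more than 5 days after the final dose of study drug will be excluded from the above described tables". Such events are listed only, except those that led to discontinuation from the study. Section 10.3 has a different general limit for efficacy and safety summaries, the "last study visit or 30 days after the permanent discontinuation of study drug". Section 10.3.3 is looser again: "Safety analyses or summaries will include all available data, as appropriate".

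**Precedence.** SAP section 1 says of itself: "It supersedes the statistical considerations identified in the study protocol".

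**Follow-up off drug.** SAP 6.4.2: "All subjects were allowed to continue in the study until the close of study, whether on IMP or not". SAP 6.12: "Subjects were not required to discontinue from the study after meeting a primary endpoint". Protocol 2.1 expects study drug to continue until an IV or SQ prostanoid is added or the subject has a lung transplant.

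**Collection.** Protocol 7.12.1 collects AEs to the end of participation. Protocol 7.12.2 extends this to 7 days after the last study visit for new AEs and 30 days for new SAEs.

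**The concern.** A treatment-emergent table is meant to describe events that exposure to the assigned drug could plausibly have caused. In this trial a subject can stop study drug, start a parenteral prostacyclin and remain under observation. Under SAP 7.2.1, a serious event months after the last tablet still meets the definition and is counted in the column of the randomized drug actually received.

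The events at issue can resemble the ones the table should detect. Protocol 7.12.8 names bleeding and hypotension as prostacyclin class risks. Protocol section 3 names bloodstream infection and local site reactions as risks of other routes that would not be expected with the oral drug. If off-drug time differs between arms, the TEAE tables mix the effect of study drug with the effect of whatever followed it, and the mixture differs by arm. What is at stake is the reading of the main by-arm safety tables. The time-to-clinical-worsening test does not use them.

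**Working it through.** **1. The window under each rule**

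| Source | Start | End for the tables |
|---|---|---|
| SAP 7.2.1 | First dose | None stated; in practice the end of collection (Protocol 7.12.2) |
| Protocol 10.11.1 | New or worse than baseline | 5 days after final dose, except events causing study discontinuation |
| Protocol 10.3 | Randomization | Last study visit, or 30 days after permanent discontinuation of drug |
| Protocol 10.3.3 | Not stated | All available data, as appropriate |

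Because the SAP supersedes the protocol's statistics and repeats none of these end dates, the first row governs. Its practical end is tied to the last visit, not to the last dose. For a subject who stays on drug to the last visit the practical end is at most 30 days later. For a subject followed off drug the two rules differ by the whole off-drug period, less 5 days.

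**2. How much off-drug time could there be?** The documents give no figure on this point, so this is a bound built from the planning inputs.

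Inputs (SAP 3.1 and 4.1): one-year worsening 45% placebo and 25% esuberaprost; proportional hazards; accrual 1.5 years; 120 per arm; stop at 113 events. My additions: exponential times, uniform accrual, no dropout.

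- Hazards: h = −ln(1 − 0.45) = 0.598 and −ln(1 − 0.25) = 0.288 per year. HR = 0.288/0.598 = 0.481.
- Check against the plan: events = 4(2.576 + 1.282)²/(ln 0.481)² gives 112, against the stated 113. Power with 113 events at two-sided 0.05 is 97.3%, against the stated 97%. The hazards match the plan.
- Probability of worsening by study time T, with follow-up uniform from T − 1.5 to T: P = 1 − [exp(−h(T − 1.5)) − exp(−hT)]/(1.5h).
- At T = 2.5 years: P = 0.637 and 0.391, or 76.4 + 46.9 = 123.3 events. The trial stops at 113, so T must be shorter.
- Solving 120(P₁ + P₂) = 113 gives T = 2.29 years, with P = 0.589 and 0.353 (70.6 + 42.4 = 113.0 events).
- Mean follow-up per subject: T − 0.75 = 1.541 years. Mean time before worsening: P/h = 0.984 and 1.227 years. Mean time after worsening: 0.557 and 0.314 years.
- Per arm: 120 × 0.557 = 66.8 and 120 × 0.314 = 37.6 person-years, about **67 v 38** (ratio 1.77).

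**3. Why this is an upper bound**

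- The clock starts at worsening, not at last dose. Subjects who worsen without starting a parenteral prostanoid are expected to stay on drug, and that time counts under either rule.
- Deaths are worsening events but are credited here with follow-up to study close.
- Dropout is set to zero, while SAP 6.4.2 cites roughly 20% premature termination in comparable trials.
- Protocol 7.10.1 and 7.10.2 say participation runs until a worsening event is confirmed, which would shorten this time.

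For scale only: if 40% of worsened subjects stopped drug at worsening and stayed in follow-up (an assumption; the documents give no share), off-drug time would be 0.4 × 66.8 = 27 v 0.4 × 37.6 = 15 person-years. At 20% it is 13 v 8, and at 60% it is 40 v 23.

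**4. What cannot be computed.** The bound covers only off-drug time that follows worsening. Subjects who stop for intolerance may be more numerous on esuberaprost and would push the other way. The documents give no stopping rates and no serious-event rates on or off drug, so no defensible percentage for the serious-TEAE row can be derived.

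**The case against.** The strongest reply is that the missing sentence is a table convention. The protocol's own TEAE definitions (7.12.8 and 10.11.1) also have no end, and the 5-day rule is a separate inclusion rule. It could appear in the data-conventions addendum promised in SAP 6.2 or in the table mock-ups mentioned in SAP section 1, neither of which was available here. That is possible, but nothing in the SAP says the addendum will set a TEAE window.

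An inclusive window also has merit: it does not hide late harm, and safety is descriptive with no formal testing (SAP 7). This stands as a reason to keep a whole-study view. It does not justify calling off-drug events treatment-emergent.

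A reader might infer more than the text supports in four ways:

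- *That the window never closes.* Protocol 7.12.2 closes collection at 7 or 30 days after the last visit.
- *That programmers face two competing rules.* The SAP supersedes the protocol's statistics, and Protocol section 10 allows such changes without amendment. One rule governs, and the point is that it yields a less useful table.
- *That this row is all the SAP shows on serious outcomes.* SAP 6.14.5 commits to deaths by category and arm, and 6.12.7 to PAH hospitalization as a component analysis. The relatedness tables may also help separate some line-related events.
- *That the tables will be biased in favour of esuberaprost.* A subject already counted for an on-drug serious event, such as a PAH hospitalization, adds nothing to the row later, and intolerance stops work the other way. The sign is not known.

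**Conclusion.** The point holds. As written, SAP 7.2.1 drops the protocol's 5-day table cut-off without replacement, and in a design that allows follow-up off study drug this makes events long after the last dose treatment-emergent in all tables of SAP 7.2.7 to 7.2.9. The size is bounded only loosely: at most about 67 v 38 person-years (placebo v esuberaprost) of off-drug time due to worsening, given the planned rates, exponential times, 113 events, 120 per arm and no dropout. The true figure is probably well below that. The effect on any reported percentage, in size or direction, is not known from the documents. The primary inference is not affected. This is a cheap improvement to the safety reporting, not a flaw in the trial's main conclusion.

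**What to change.** In SAP 7.2.1, or in the pre-unblinding addendum, limit the TEAE tables in 7.2.7 to 7.2.9 to events with onset or worsening from the first dose to 5 days after the last dose. Keep the protocol's exception for events that caused discontinuation from the study. If another window is preferred, such as the 30 days in Protocol 10.3, state it with the reason and record it as a departure from Protocol 10.11.1.

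Add two tables by treatment group: all serious events over the whole study, whatever the time since last dose, and serious TEAEs by SOC and preferred term.

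The cost is one sentence, one derived flag (AE onset date minus last-dose date) and two tables from data already collected. The drawback is that a short window can miss delayed harm, and the whole-study table covers that for serious events.

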7.2.9 Subgroup Analysis

TEAEs will be summarized similarly within subgroups: male, female, <65 years old, \geq 65 years old, Caucasian, Non-Caucasian, and each PAH etiology. Other subgroups may be examined if suggested by the data.

7.2.10 Clinical Laboratory Evaluations

Laboratory tests for serum chemistry, hematology, coagulation, urinalysis, and pro-NT-BNP were performed by a certified central laboratory [REDACTED], [REDACTED], and laboratory results were forwarded to the site. Electronic data were automatically uploaded weekly into the subject's eCRF as specified with the eCRF vendor and [REDACTED].

If a clinical site used a local laboratory instead of the central laboratory, the local laboratory will provide the values to the investigator and the sponsor. These data will be included into the database. Results will be transformed for consistency into the same units and normal ranges used by the study's central laboratory ([REDACTED]), applying the formula:

$$y = (x - Li) \frac{Uc - Lc}{Ui - Li} + Lc$$

where x = original value, Li and Ui = lower and upper limits of normal for individual laboratory, Lc and Uc = lower and upper limit for central laboratory

If the lower limit of the central laboratory is 0, values below the lower limit of normal for a laboratory value prior to transformation will be assigned the value 0. If there is no upper limit for a test, the following formula will be used:

$$y = (x - Li) \frac{Lc}{Li} + Lc$$

In cases of missing units for a test, missing limits of central laboratory or an alternative test is performed than specified in the study protocol (e.g., absolute value instead of percent for hematology), transformed values will be set to missing; however, the non-missing flags for clinically significant values, as defined by the investigator, will be retained with transformed values for summaries. Transformed results for clinical laboratory tests will be used for all summaries and presentations. Summaries and presentations will be made using standard units.

Descriptive statistics for each clinical laboratory parameters (hematology, serum chemistry and coagulation) will be presented by treatment group at baseline, each post-baseline assessment, and End of Study visits for raw data and change from baseline (see Section 6.3.2).

Post-baseline clinically significant values, as defined by the investigator, for hematology, serum chemistry, coagulation, and urinalysis parameters will be summarized as transition tables from baseline to each post-baseline assessment and End of Study visits.

Tables will contain the number and percentage of subjects by treatment group with post-baseline clinically significant categories (low, high, and normal for hematology, chemistry, and coagulation; abnormal and normal for urinalysis) compared to baseline category for each parameter.

7.2.11 Vital Signs

Descriptive statistics for vital signs (temperature, heart rate/pulse, systolic blood pressure, diastolic blood pressure, respiration rate, weight, height, BMI) will be presented by treatment group at baseline, at each post-baseline assessment, and End of Study visits for the raw data and change from baseline.

7.2.12 ECG Evaluations

Descriptive statistics for ECG findings (heart rate, PR interval, QRS interval, QT interval, QTc interval (original and standardized across reports), sinus rhythm (normal, abnormal), ECG results (normal, abnormal), abnormality reported) will be presented by treatment group, at baseline, at each post-baseline assessment, and End of Study visits for raw data and change from baseline (see Section 6.3.2). Whenever more than one ECG are read occurs on the same day, the data summaries will use the average of these readings.

In addition, a summary of subjects with treatment-emergent clinically significant values will be presented by treatment group. Presentation will be made in order of decreasing incidence by type of abnormality with the number and percentage of subjects who experienced the type of abnormality.

7.3 Physical Examinations

Any value the Investigator judges to be a clinically significant abnormal change after the subject's consent to the study was to be recorded as an AE.

7.4 Interim Analyses and Data Monitoring

[figure not shown]
No formal interim efficacy analyses were planned or conducted.

An independent external statistical group (██████████) performed interim safety analyses. Only the Data Safety Monitoring Board reviewed these data in order to monitor the safety of the subjects in the study. Lung Biotechnology and all other employees of ██████████ ██████████ remained blinded throughout the conduct of this study.

